For all women who undergo VIA, we will determine if a woman is VIA-positive and ablation-eligible using colposcopy with Mobile ODT EVA system. Women who are VIA-positive will undergo colposcopically-directed biopsies of the acetowhite lesion, with at least 2 and up to 4 biopsies taken, as well as an ECC. If the woman is still considered to be ablation-eligible by colposcopy, she will then undergo thermocoagulation. Women who are VIA-negative will also undergo colposcopy, and at least 2 and up to 4 cervical biopsies and ECC if a lesion is seen at colposcopy. Thermocoagulation will also be performed on these women if they are found to have an ablation-eligible lesion on colposcopy. If no lesion is seen on colposcopy, the woman will have cervical pap smear and ECC collected, and no thermocoagulation will be performed. Women who are suspicious for cancer at VIA will undergo colposcopically-directed cervical biopsies. Whenever biopsy is indicated, we will perform at least 2 cervical biopsies on women because previous studies have shown that cervical biopsy is most sensitive when at least 2 biopsies are taken. During colposcopy, images of the cervix may be captured with the EVA system. These images will be stored only in password-protected and de-identified study databases, linked only to the study participant PID. The images will be used for internal quality assurance and may also be shared with the sponsor or other parties for research purposes.

For women to undergo thermocoagulation, we will consider them to be ablation-eligible if the following criteria are met at colposcopy: 1) cervical lesions are not suspicious for ICC; 2) cervical lesions are located entirely on the ectocervix; 3) cervical lesions are no more than 2-3 mm into the endocervical canal; 4) the entire squamocolumnar junction (SCJ) can be visualized; and 5) all visible lesions are deemed appropriate for thermocoagulation by the treating provider. Women with suspected endocervical dysplasia, CIS, or ICC will be referred for treatment at the Kamuzu Central Hospital (KCH), a public tertiary and teaching hospital Colposcopy Clinic on which campus UNC Project-Malawi is situated.

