women who are HPV positive/VIA positive/ablation-eligible, and undertreatment among HPV positive/VIA negative women. All HPV positive women and every 10th consecutive HPV-negative woman will undergo VIA. During VIA, we will determine if a woman is VIA-positive and ablation-eligible. Women who are VIA-positive will undergo colposcopically-directed cervical biopsies and endocervical currettings (ECC). If the woman is still considered to be ablation-eligible by colposcopy, she will then undergo thermocoagulation. Women who are VIA-negative will also undergo colposcopy, but they will only have cervical biopsies and ECC performed if a lesion is seen on colposcopy. Following VIA, we will collect directed cervical biopsies and ECC from VIA positive women prior to thermocoagulation treatment if ablation-eligible by colposcopy, or cervical pap smear and ECC from VIA negative women if no lesion is seen at colposcopy. If a lesion is seen at colposcopy, VIA negative will also undergo colposcopically-directed cervical biopsy and ECC. We hypothesize that <25% of HPV positive/VIA positive women would have been overtreated (no CIN2+, but treated) and that <30% of HPV positive/VIA negative women would have been undertreated (CIN2+, but untreated).

Data analysis for secondary objective I: Overtreatment will be calculated as the proportion of HPV positive/VIA positive/ablation-eligible women who would have been treated with thermocoagulation based on their HPV and VIA findings alone (without colposcopy), but were found to have no CIN2+ on colposcopically-directed cervical biopsy or ECC at Screening/Enrollment. This proportion will represent the women with no lesions or low-grade lesions (CIN1) who would have been unnecessarily treated if we based the decision to perform thermocoagulation on HPV and VIA testing alone.

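### Overtreatment is meant to describe treatment decided without colposcopy, but its denominator depends on ablation-eligibility, whose only criteria are applied at colposcopy, and the plan carries conflicting denominators

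*Combined protocol and SAP*

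**What the plan says.** Section 6.3, Secondary objective I, gives the denominator: "Overtreatment will be calculated as the proportion of HPV positive/VIA positive/ablation-eligible women". It restricts the measure to those "who would have been treated with thermocoagulation based on their HPV and VIA findings alone (without colposcopy", and counts a woman as overtreated if biopsy or ECC at enrolment shows no CIN2+. On interpretation it adds: "This proportion will represent the women with no lesions or low-grade lesions (CIN1".

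The protocol's only list of eligibility criteria is in Section 4.3, Screening & Enrollment: "we will consider them to be ablation-eligible if the following criteria are met at colposcopy". The same section says "we will determine if a woman is VIA-positive and ablation-eligible using colposcopy with Mobile ODT EVA system".

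Section 6.3 words the corresponding step differently: "During VIA, we will determine if a woman is VIA-positive and ablation-eligible". It continues: "If the woman is still considered to be ablation-eligible by colposcopy, she will then undergo thermocoagulation". No criteria for a VIA-stage judgement appear anywhere.

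The hypothesis in Section 6.3 is that fewer than 25% of HPV-positive/VIA-positive women would have been overtreated. It carries no eligibility condition.

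**The concern.** The measure should tell a programme that treats on HPV and VIA results, with no colposcope, how many women it would treat without need. If eligibility is read as Section 4.3 defines it, a colposcopic finding decides who is counted. A VIA-positive woman in whom colposcopy shows nothing can then leave both numerator and denominator, although such a programme would treat her. If her tissue is normal, she is also among the women Section 6.3 says the proportion represents.

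With the hypothesis included, there are three candidate denominators: eligible at colposcopy, eligible at VIA, and all HPV-positive/VIA-positive women. The plan does not choose among them. Section 1.3 says the study is to inform national policy, so the figure needs one stated meaning.

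**Working it through.** **Texts side by side.** Sections 1.1, 2.1.1, 4.1 and 6.1 tie ablation-eligibility to colposcopy when describing the strategy, and Section 5.1 footnote 5 ties treatment to an eligible lesion seen at colposcopy. The overtreatment wording in Sections 2.2.1, 6.1 and 6.3 omits colposcopy. That omission does not settle the matter. Among the completion indicators in Section 6.3, the same-day treatment line names colposcopy and the next line, on later-day treatment, does not, though the group appears to be the same. The indicator that splits VIA-positive women lists thermocoagulation-eligible, LEEP-eligible and suspected cancer, with no category for a woman without a colposcopic lesion.

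**Inputs.**
- HPV-positive women (Section 6.2): 313 + 125 = 438.
- CIN2/3 (Section 6.2): 625 × 0.50 × 0.20 = 62.5, taken as 63; 625 × 0.20 × 0.10 = 12.5, taken as 13; total 76. This reproduces the plan's figure.
- HPV-positive without CIN2/3: 438 − 76 = 362.
- VIA sensitivity 0.69 (0.54–0.81) and specificity 0.87 (0.79–0.92), from Section 6.3.

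**All HPV-positive/VIA-positive women.**
- True positives, TP = 0.69 × 76 = 52.4.
- False positives, FP = (1 − 0.87) × 362 = 47.1.
- Overtreatment = FP / (FP + TP) = 47.1 / 99.5 = 47.3%. Over the corners of the two confidence intervals it runs from 32.0% to 64.9%.

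The 25% bound has no stated formula and rests partly on a pilot false-positive rate that is not given, so it cannot be reproduced. One minus specificity is 13% (8% to 21%), which lies below 25%, but its denominator is women without CIN2+, not VIA-positive women.

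**Effect of a colposcopic condition.** Let a share f of VIA-positive women without CIN2+ and a share g of those with CIN2+ drop out. Then overtreatment = FP(1 − f) / [FP(1 − f) + TP(1 − g)]. It is below 47.3% when f > g and above it when f < g. The documents give neither share, so the values below are assumptions.

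| f | g | Overtreatment |
|---|---|---|
| 10% | 0 | 42.4 / 94.8 = 44.7% |
| 25% | 0 | 35.3 / 87.7 = 40.2% |
| 50% | 0 | 23.5 / 76.0 = 31.0% |
| 25% | 25% | 35.3 / 74.6 = 47.3% |
| 10% | 25% | 42.4 / 81.7 = 51.9% |

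With g = 0, reaching 25% requires f = 1 − (52.44 / 3) / 47.06 = 62.9%.

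**The case against.** The best defence is that the plan already intends a VIA-stage denominator. Section 6.3 places a determination during VIA. The word *still*, in both Section 4.3 and Section 6.3, presupposes an earlier judgement. The overtreatment definition expressly sets colposcopy aside, and the hypothesis has no eligibility condition. This stands as a plausible reading. It does not resolve the conflict, because no VIA-stage criteria exist and Section 4.3 describes the parallel step as done with the colposcope.

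A reader might infer that VIA-positive women without a colposcopic lesion are certain to be excluded. The documents do not establish that. None of the five criteria in Section 4.3 expressly requires a lesion, although Section 5.1 footnote 5 speaks of one. Sampling is also inconsistent. Section 6.3 biopsies VIA-positive women and links Pap smear with ECC to VIA-negative women without a lesion, while Section 4.3 says generally: "If no lesion is seen on colposcopy, the woman will have cervical pap smear and ECC collected, and no thermocoagulation will be performed". Section 4.2 and Section 5.1 footnote 4 make the same general split between biopsy and Pap smear.

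A reader might also infer that the bias must run downwards and help meet the 25% hypothesis. That is not supported either. Colposcopic ineligibility can also remove women whose lesion extends too far into the canal or whose squamocolumnar junction is not visible. Some of them will have CIN2+, and losing them raises the proportion. Women already suspicious for cancer at VIA do not add to this offset, since they would leave the proposed denominator too.

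Finally, the measure is secondary and described as largely descriptive, without a power calculation. That limits the consequence but does not remove the need for one definition.

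**Conclusion.** The inconsistency is certain: the measure is meant to exclude colposcopy, the only written eligibility criteria are colposcopic, and the hypothesis uses a different denominator again. Whether women are in fact excluded, and in which direction the estimate moves, is not certain. It is understated if a larger share of women without CIN2+ than with CIN2+ drops out, and overstated in the opposite case.

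With no CIN2+ women dropping and 10% to 50% of false positives dropping, the shift is 2.6 to 16.3 points below 47.3%. Even at 50% the figure stays above 25% on the central inputs, so this analysis does not show that the definition would make the hypothesis succeed.

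The 47.3% assumes that VIA accuracy from primary screening holds among HPV-positive women, which Section 6.3 itself cautions about. It also assumes that all 76 CIN2/3 cases are HPV-positive and that CIN2+ is approximately CIN2/3.

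**What to change.** - Make the primary denominator all HPV-positive/VIA-positive women not suspicious for cancer at VIA. Alternatively, use women eligible at a VIA-stage judgement recorded before colposcopy, with its criteria written down.
- State the under-25% hypothesis for that same denominator.
- Keep women with no colposcopic lesion in the denominator. Classify them by the biopsy, ECC or cytology available, and add a sensitivity analysis for those without biopsy, since counting them by default as free of CIN2+ could push the figure up.
- Report the colposcopy-eligible version as a secondary analysis.
- Reconcile Sections 4.2, 4.3, 5.1 (footnote 4) and 6.3 on which samples a VIA-positive woman with no colposcopic lesion gives.

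The cost is mainly SAP wording. The first denominator should need no new data item. The second needs the VIA-stage judgement on the form, and the case report forms are not in the documents, so whether it is already there cannot be checked. The overtreatment figure may look less favourable.

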#### **Week 4**

All women who had cervical biopsies or cervical pap smear, and ECC done at Screening/Enrollment will return for histology and/or cytology results at Week 4. HPV-positive/VIA-negative women without CIN or ICC on histology and those with normal cytology will be advised to continue with routine ICC screening per guidelines. Women who underwent thermocoagulation will be evaluated for interval medical history or post-treatment adverse events during this visit. HPV-positive/VIA-negative women with CIN2+ on ECC or abnormal cytology on cervical pap smear will be referred to KCH Colposcopy Clinic for further management.

HPV-positive/VIA-positive women who had CIN detected at baseline cervical biopsy, and underwent thermocoagulation will be followed up at Week 24 post-treatment. Women who had CIN and visible cervical lesion that was not ablation-eligible by colposcopy or had ICC will be referred to KCH Colposcopy clinic for further management.

Women who are HPV-positive may be enrolled in and consented for IDIs at their Week 4 visit. These interviews will be conducted similarly to those done at the Screening/Enrollment visit but they will also cover women's experiences sharing their screening results with others and abstaining from sex for the recommended interval after biopsy/thermocoagulation.

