## 5.0 TIME AND EVENTS TABLE

### 5.1 Schedule of study procedures

Study Visit	Screening & Enrollment	Week 4	Week 24	Week 28
Women who will attend the study visit	All women	Women who had cervical biopsy or cervical pap smear, and ECC done at Screening & Enrollment	Women who had CIN1+ at Screening & Enrollment and underwent thermocoagulation	Women who attended the Week 24 Visit
Evaluations				
Informed consent	X			
Baseline survey	X			
Urine pregnancy testing	X	X	X	
HIV-1 Rapid Test (2 kits)	X			
HIV-1 Confirmatory Test 	X			
CD4+ T cell count 	X			
HIV-1 RNA (plasma) 	X			
Self-collected vaginal brush	X			
hr-HPV testing of self-collected samples	X		X	
hr-HPV and S5 methylation testing of urine sample	X			
Provider-collected cervical brush	X 		X	
hr-HPV testing of provider-collected cervical sample	X 			
S5 methylation testing of provider-collected cervical sample	X 			
VIA 	X			
Colposcopy and cervical biopsy or cervical pap smear, and ECC 	X		X	
Thermocoagulation 	X			
Thermocoagulation-related adverse events evaluation		X		
Provide results and any referrals		X		X
Follow-up questionnaire 		X		
Enroll for IDIs	X	X		

For those with discordant HIV rapid tests.

For HIV-positive participants only

For all hr-HPV+ and for every 10th woman who is hr-HPV-.

Cervical biopsy and ECC if lesion seen at colposcopy; Cervical pap smear and ECC if no lesion seen at colposcopy

For women with ablation-eligible cervical lesion at colposcopy.

For follow-up of cervical histology and/or cytology results from Screening/Enrollment and to assess for any change in history or adverse events from thermocoagulation (if thermocoagulation was performed).

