Undertreatment will be calculated as the proportion of women with CIN2+ at Screening/Enrollment who were not treated or referred via our screening algorithm due to a negative HPV and/or VIA result. This proportion will represent the women with CIN-2+ who were missed by our HPV-and-VIA-based algorithm. For undertreatment, we will also evaluate the proportion of women who underwent thermocoagulation but were ECC positive for endocervical CIN2+, and therefore needed to be referred for further management since thermocoagulation does not adequately treat endocervical dysplasia. We have based our hypotheses on a recent review, which found that the pooled estimates for VIA sensitivity and specificity were 0.69 (95% CI 0.54-0.81) and 0.87 (95% CI 0.79-0.92), respectively, as well as from the high false positive rate for VIA found in our pilot study with nurses and clinicians in Malawi. These performance measures, however, were for primary screening, rather than as referral to treatment among HPV positive women.

In addition, to assess the potential for undertreatment of HPV-positive women, we will conduct VIA at Screening/Enrollment for every 10th women who is hr-HPV

negative. This sub-set analysis of HPV negative women undergoing VIA will allow us to control for potential verification bias. As all women will not be referred for verification by colposcopy, using only the histology results on HPV positive women to estimate disease burden could lead to biased inference. To correct for this verification bias, we will utilize the colposcopy results among the random sub-set of HPV-negative women to employ the maximum likelihood method proposed by Zhou. Estimates using this method are valid provided that the histology data are missing at random. This assumption means that for women with the same test results, those who were referred to colposcopy were similar to those that were not. Corrected CIN2+ burden will be estimated using maximum likelihood estimators (MLEs). This secondary objective is largely descriptive and, thus, formal power calculations are not made.

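### Ectocervical CIN2+ cannot be confirmed in VIA-negative women with no colposcopic lesion, and the planned verification-bias correction does not repair the resulting undertreatment estimate

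*Combined protocol and SAP*

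**What the plan says.** All references are to the combined protocol and SAP.

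- **Specimens when no lesion is seen.** Section 4.3 (Screening & Enrollment) says: "If no lesion is seen on colposcopy, the woman will have cervical pap smear and ECC collected, and no thermocoagulation will be performed". Footnote 4 of section 5.1 agrees: "Cervical pap smear and ECC if no lesion seen at colposcopy". So does section 4.2.
- **Two statements in section 6.3, secondary objective I.** On VIA-negative women, one sentence says "they will only have cervical biopsies and ECC performed if a lesion is seen on colposcopy". A later sentence plans "cervical pap smear and ECC from VIA negative women if no lesion is seen at colposcopy". The first gives a lesion-free woman no ECC; the second does.
- **What counts as disease.** The overtreatment definition rests on "no CIN2+ on colposcopically-directed cervical biopsy or ECC at Screening/Enrollment", so ECC counts as histology and cytology is not named. The undertreatment definition refers to CIN2+ at enrolment and names no specimen.
- **After the Pap smear.** Under Week 4 in section 4.3, "HPV-positive/VIA-negative women with CIN2+ on ECC or abnormal cytology on cervical pap smear will be referred to KCH Colposcopy Clinic". Section 6.3 has no rule on whether histology from that referral enters the estimate.
- **The correction.** Section 6.3 applies the Zhou maximum likelihood method, using colposcopy results from the sampled HPV-negative women, with the condition "Estimates using this method are valid provided that the histology data are missing at random". It explains the condition as similarity, given test results, between women who were and were not referred to colposcopy.
- **The denominator.** The hypothesis of less than 30% undertreatment refers to HPV-positive/VIA-negative women. The calculation that follows divides by women with CIN2+.

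**The concern.** Undertreatment counts disease among women the algorithm would have left untreated, and these are mostly VIA-negative women. They are also the women whose verification is weakest. VIA-positive women have at least two directed biopsies plus ECC. VIA-negative women are biopsied only if colposcopy shows a lesion. The reference standard therefore differs by the result of the test being evaluated.

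On the undertreatment definition in section 6.3, a missed case of ectocervical CIN2+ drops out of both numerator and denominator, and the algorithm looks safer than it is. Section 1.3 says the results will inform national policy, so a falsely reassuring miss rate would matter. The only correction planned concerns a different group, the HPV-negative women who never reach colposcopy. All HPV-positive/VIA-negative women are planned to have colposcopy, so that correction does not touch them.

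**Working it through.** **1. The plan's own count (section 6.2).**
- HIV-positive: 313 HPV-positive × 0.20 = 62.6, rounded to 63.
- HIV-negative: 125 HPV-positive × 0.10 = 12.5, rounded to 13.
- Total: 63 + 13 = 76 women with CIN2/3 among 313 + 125 = 438 HPV-positive women. This reproduces the stated 76, used below as the CIN2+ count.

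**2. Split by VIA (section 6.3: sensitivity 0.69, specificity 0.87).**
- CIN2+: VIA-positive 76 × 0.69 = 52.44; VIA-negative 76 × 0.31 = 23.56.
- No CIN2+ (438 − 76 = 362): VIA-negative 362 × 0.87 = 314.94.
- HPV-positive/VIA-negative in all: 23.56 + 314.94 = 338.5.

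**3. True undertreatment among HPV-positive women.**
- Denominator women with CIN2+: 23.56 / 76 = 31.0%.
- Denominator HPV-positive/VIA-negative women: 23.56 / 338.5 = 7.0%.

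**4. Lesion-free women coded disease-free unless ECC is positive.** Let d be the share of CIN2+ in VIA-negative women that biopsy and ECC detect together. The documents give no value; 0.6 to 0.8 is an assumption. Detection in VIA-positive women is taken as complete. The estimate is 23.56d / (52.44 + 23.56d).
- d = 0.6: 14.14 / 66.58 = 21.2%.
- d = 0.8: 18.85 / 71.29 = 26.4%.
- The estimate equals 30% at d = (0.30 × 52.44) / (0.70 × 23.56) = 15.73 / 16.49 = 0.954, so any detection rate below about 95% puts it under 30%.

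On the other denominator, missed cases leave the numerator only: 14.14 / 338.5 = 4.2% and 18.85 / 338.5 = 5.6%, against a true 7.0%.

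**5. Lesion-free women treated as unverified.** Suppose prevalence in biopsied women is extrapolated to lesion-free women given HPV and VIA alone, setting ECC aside. Let c be the probability that a lesion is seen in a VIA-negative woman with CIN2+ (assumed 0.5 to 0.9), and f the same without CIN2+ (assumed 0.1 to 0.4).
- Example, c = 0.7 and f = 0.2: lesions are seen in 16.49 women with and 62.99 without CIN2+, so prevalence is 16.49 / 79.48 = 20.7%. Extrapolated cases are 0.2075 × 338.5 = 70.2, and the estimate is 70.2 / (52.44 + 70.2) = 57.3%.
- Over the whole assumed range the estimate is 35.6% to 72.2%, above the true 31% throughout. The bias is upward whenever c exceeds f.

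**6. Dependence on the VIA sensitivity.** The interval quoted in section 6.3 is 0.54 to 0.81, so true undertreatment could lie between 1 − 0.81 = 19% and 1 − 0.54 = 46%. With d = 0.6 to 0.8 the estimates become 12.3-15.8% and 33.8-40.5%. The bias in step 4 stays downward, but it crosses 30% only when true undertreatment is somewhat above 30%.

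**The case against.** The strongest reply is that the quoted condition concerns referral to colposcopy. Every tenth consecutive HPV-negative woman is selected regardless of disease, and every woman who has VIA also has colposcopy. Missing at random, as section 6.3 defines it, is then plausible by design. This stands. A reader might infer that the assumption fails; for the step the plan corrects, the documents do not support that. The problem is an imperfect reference standard among women already counted as verified.

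Second, lesion-free women are not without histology: most of the relevant text gives them ECC, and ECC counts towards CIN2+. This also stands, and it confines the gap to ectocervical disease.

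Third, a reader might infer that undertreatment is simply biased downward. The plan does not say how lesion-free women are coded. Downward is the likelier reading, because section 6.3 speaks of verification by colposcopy and groups women without lesions with those who have no CIN2+. Step 5 shows that the other coding reverses the direction.

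Fourth, the undertreatment definition does not exclude cytology or referral histology, and referred women are followed up at Week 24. True, but silence leaves the choice to be made after the data are seen.

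Fifth, the 0.69 comes from primary screening, as the plan itself warns, and the objective is descriptive, with no power calculation. Both points limit how firmly the size can be stated. Neither removes the need to define the estimate.

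**Conclusion.** The point holds in a limited form. Study histology cannot confirm ectocervical CIN2+ in VIA-negative, lesion-free women; the plan does not define their disease status; and the Zhou correction does not address this.

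With VIA sensitivity 0.69 and women with CIN2+ as the denominator, a true 31% would be reported as about 21-26% if lesion-free women are coded disease-free and 60-80% of CIN2+ in VIA-negative women is detected. It would be overstated if they are treated as missing and extrapolated from HPV and VIA alone. The detection rates are assumptions.

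On that denominator the downward bias can move the result from just above to below the plan's 30% threshold. The hypothesis itself is worded with the other denominator, on which about 7% is expected and 30% is never approached. Until the denominators are reconciled, the threshold has no single meaning.

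**What to change.** In section 6.3, secondary objective I:

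1. State that the primary CIN2+ status of lesion-free women rests on ECC, and do not describe the Zhou-corrected estimate as free of verification bias.
2. Add a secondary analysis that also counts CIN2+ histology obtained after referral for abnormal cytology and, as a separate version, high-grade cytology. Note that Pap smears are taken only in lesion-free women, so false positives fall mainly on the VIA-negative side and can inflate undertreatment.
3. Add a sensitivity analysis over the assumed detection rate of CIN2+ in all lesion-free women, including those with normal cytology. Varying only the cytology-abnormal women would leave the remaining missed cases outside the range.
4. Reconcile the two sentences on whether lesion-free VIA-negative women have ECC, and choose one undertreatment denominator for both hypothesis and calculation.

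Stratifying the correction by whether a lesion was seen is not a substitute: the lesion-free stratum has no ectocervical biopsies, so its ectocervical prevalence is not identified.

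The cost is SAP wording, linkage to results from the referral clinic on the same campus, and some extra analysis. The cytology is already planned, and section 4.3 already follows up referred women. The downside is that cytology is a less specific standard, so the versions with and without it should be reported side by side.
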